4.2.3.3 Clinical Benefit Rate (CBR)

The CBR is defined as the percentage of patients with the best measurement of response categorized as CR, PR or SD. Note that SD requires no confirmation as is required for the best overall response of either CR or PR. The first tumor assessment is planned to occur 9 weeks after first dose and therefore, iSD documented at the first assessment would typically qualify as iSD. However, an iSD with actual assessment time less than 6 weeks after first dose will not be qualified as iSD. Patients with no post-baseline tumor assessments are considered to have achieved no clinical benefit.

4.2.3.4 Time to response

The time to response is defined as the length of time from start of treatment until the date of the first documented CR or PR assessed through RECIST 1.1. CR or PR requires confirmation on imaging dates that are at least 4 weeks apart. Once it is confirmed, the first documented CR or PR will be considered the start of the response.

Patients not obtaining an overall response (CR or PR) will be censored at the the date of their last tumor assessment.

4.2.3.5 Duration of response

Duration of response will be calculated as the length of time from the first date of confirmed CR/PR to the date of death or the date of first documented tumor progression (PD), whichever is earlier, using RECIST v1.1. Patients who remain alive and do not progress are censored on the date of their last tumor assessment. Response duration is only evaluated in patients with an overall response of CR or PR.

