9.1.3 On-Study Tumor Imaging

Following the screening CT scans, patients are to have repeat radiological assessments at the end of Cycle 3 [9 weeks (63 days \pm 3 days) from Cycle 1 Day 1]. Subsequent radiological assessments are to be performed every 9 weeks (at the end of every 3rd treatment cycle) until documentation of disease progression. If cycles become delayed, for whatever reason, the imaging schedule will as a default follow a nine-week pattern regardless of where in terms of cycles the subject is. If there is a large mismatch the PI can discuss frequency with the medical monitor

Per RECIST 1.1, if a patient has a documented partial or complete response, a

confirmatory tumor radiological assessment is to be performed not less than 4 weeks from the date the response was first documented.

Patients are to continue to have tumor assessments performed until whichever of the following occurs first:

- Site-assessed disease progression is documented
- The start of new anti-cancer treatment
- Withdrawal of consent
- Death
- The end of the study

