- For a **clinically stable** subject with first radiologic evidence of progressive disease by RECIST 1.1 (i.e., **unconfirmed progression of disease or iUPD**), it is at the discretion of the site investigator to continue treating the subject with the assigned treatment per protocol until progression of disease (iCPD) is confirmed at least 28 days from the date of the scan first suggesting PD. If radiologic progression is confirmed by subsequent scan then the subject will be discontinued from trial treatment. If radiologic progression is not confirmed by iRECIST per the site, then the patient should resume or continue trial treatment and have their next tumor imaging according to the protocol schedule of every 9 weeks (end of every 3rd treatment cycle) until progression is confirmed at a later timepoint by the site. In applying iRECIST, the appropriate documentation at

each time point must be made (i.e. iSD, iUPR, iUCR). For a more comprehensive and detailed account of the application of RECIST 1.1 and iRECIST for in-study imaging assessments please refer to the imaging guide document Note that RECIST 1.1 must always serve as the primary imaging assessment guide up to the first indication of disease progression after which iRECIST may be used as described.

- Any subject deemed **clinically unstable** should be discontinued from trial treatment at 1st radiologic evidence of PD and is not required to have repeat imaging for PD confirmation.
- In subjects who discontinue study therapy without documented disease progression, every effort should be made to continue monitoring their disease status by tumor imaging using the same imaging schedule used while on treatment (every 9 weeks), until (1) the start of new anti-cancer treatment, (2) disease progression (3) death, or (4) the end of the study, whichever occurs first.

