4.2.3 Definition of Efficacy Endpoints

All patients will have a tumor measurement after cycle 3 (week 9) and subsequently after every third cycle. Measures will be assessed through RECIST 1.1 until whichever of the following occurs first:

- Site-assessed disease progression is documented
- The start of new anti-cancer treatment
- Withdrawal of consent
- Death
- The end of the study

After progression, measures will subsequently be analyzed through iRECIST as an exploratory endpoint.

The outcome of a tumor measurement for RECIST 1.1 is a categorization into one of the following categories:

- CR – Complete Response
- PR – Partial Response
- SD – Stable Disease
- PD – Progressive Disease
- Non-CR/Non-PD
- Not Evaluable

For iRECIST, a tumor measurement is categorized into one of the following:

- iCR
- iPR
- iSD
- iUPD
- iCPD
- Non-iCR/Non-iPD
- Not Evaluable

Note that RECIST 1.1 and iRECIST is equivalent until Progressive Disease (PD).

There will be two RECIST 1.1 and iRECIST categorizations, one made in the clinic and one made by an independent radiologist at MEDIAN Technologies. The categorization by the independent radiologist is the one that will be used in the analyses detailed in this SAP. The categorizations at the clinic will be reported descriptively as pure explorative purpose.

A tumour measurement may consist of scans conducted at different days (during the visit window) but there will be only one date associated to the categorization for each visit. That date will be set by the independent radiologist and will be the date used in the derivation of the time to event endpoints below. The overall process for image receipt, review and reporting conducted by MEDIAN Technologies is detailed in the Imaging Review Charter -01, dated 7 February 2018.

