4.2.3.9 Duration of iBOR

The duration of iBOR is defined as the length of time from the date when iBOR is first documented until the date of death or the date when a change in disease state using iRECIST is objectively documented, whichever is earlier. Patients who remain alive and do not change from iBOR in disease state are censored on the date of their last tumor assessment. Patients who start a new therapy and do not change from iBOR in disease state are censored at the last tumor assessment prior to initiating the subsequent anticancer therapy. Duration of iBOR is only evaluated in patients with a documented disease state.

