4.2.3.13 Duration of immune response

Duration of immune response is defined as the length of time from the first date of confirmed iCR/iPR to the date of death or the date of first documented tumor progression (iUPD) provided that iCPD is confirmed at the next assessment, whichever is earlier, using iRECIST. Patients who remain alive and do not progress are censored on the date of their last tumor assessment. Patients who start a new therapy without a prior iUPD are censored at the last tumor assessment prior to initiating the subsequent anticancer therapy. Response duration is only evaluated in patients with an overall immune response of iCR or iPR.

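### RECIST duration of response counts death as an event even after new anticancer therapy, although scans have stopped by then and both iRECIST durations censor at the last scan before it

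*SAP*

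**What the plan says.** For RECIST, SAP 4.2.3.5 states: "Duration of response will be calculated as the length of time from the first date of confirmed CR/PR to the date of death", or to first documented progression if that is earlier. The only censoring provision is "Patients who remain alive and do not progress are censored on the date of their last tumor assessment". Nothing is said about a change of therapy.

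The two iRECIST durations do say something:
- SAP 4.2.3.13, duration of immune response: "Patients who start a new therapy without a prior iUPD are censored at the last tumor assessment prior to initiating the subsequent anticancer therapy".
- SAP 4.2.3.9, duration of iBOR: "Patients who start a new therapy and do not change from iBOR in disease state are censored at the last tumor assessment" before the new therapy.

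Tumor assessment has a stop rule. SAP 4.2.3 says "Measures will be assessed through RECIST 1.1 until whichever of the following occurs first", and one of the listed stops is "The start of new anti-cancer treatment". Protocol 9.1.3 has the same rule for imaging ("Patients are to continue to have tumor assessments performed until whichever of the following occurs first"). Protocol 9.1.5 repeats it for patients who leave study therapy without progression, its first listed stop being "1) the start of new anti-cancer treatment". Under Protocol 6.3 and 6.3.3 the patient then passes to survival follow-up, with a telephone contact every 3 months.

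**The concern.** After the switch, progression is no longer looked for but death still is. A responder who starts another therapy with no progression on record can therefore have only one recorded event, death. The interval from the last scan to death, most of it possibly spent on a different drug, is then credited as response to the study combination.

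SAP 4.2.3 treats RECIST 1.1 and iRECIST as equivalent up to progression. For this patient the two response records are identical, yet one duration is an event at death and the other is censored at the last scan. The censoring rule is written out for two exploratory endpoints and missing from the secondary one. Duration of response is reported as a Kaplan-Meier median with a 95% confidence interval (SAP 5.3), possibly from very few responders, so the handling of one patient can reach the reported figure.

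**Working it through.** The plan states no expected median, event count or precision for duration of response, so there is no figure to reproduce. The check applies each rule to the same patient and then looks at the summary statistic.

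**1. The rules case by case.** Take a confirmed responder who starts new therapy with no documented progression.

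| Status at cut-off | SAP 4.2.3.5 (RECIST) | SAP 4.2.3.13 (iRECIST) |
|---|---|---|
| Alive | Censored at last scan | Censored at last scan before new therapy |
| Dead | Event at death | Censored at last scan before new therapy |

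Because scans stop at the switch, the two entries in the first row are the same date. The rules differ only for patients who switch and then die.

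**2. One patient.** Assumed: response at week 9, last scan at week 27, new therapy at week 28, no documented progression.
- As written: duration = death week − 9. Death at week 40, 60, 80 or 104 gives an event at 31, 51, 71 or 95 weeks.
- Under the 4.2.3.13 rule: 27 − 9 = 18 weeks, censored, in all four cases.

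**3. Weight of one patient.** From SAP Table 4, the smallest successful responder count is r2 + 1: 4 (colorectal), 5 (ovarian) and 6 (cervical). One patient is 1/4 = 25%, 1/5 = 20% or 1/6 = 17% of the responders.

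**4. Five responders, constructed.** Three progress at 6.2, 8.3 and 10.4 months. Two switch after last scans at 4.1 and 6.2 months and die at 14 and 18 months.
- As written, all five are events. The survival estimate falls 0.8, 0.6, 0.4, reaching one half or less at 10.4 months.
- With censoring at the switch, four are at risk at 6.2 months, so S = 3/4 = 0.75. Two are at risk at 8.3 months, so S = 0.75 × 1/2 = 0.375. The median is 8.3 months.

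**5. Direction over a range of assumptions.** None of these inputs comes from the documents except the 9-week scan interval. A large simulation measured time from response, with exponential times: median time to progression 6 or 12 months; a nominal 10%, 20% or 40% of responders switching before progression; median survival after the switch 6, 12 or 18 months; cut-off at 24 months. In the 18 settings:
- The average time added per patient who switched and died was 6.6 to 9.7 months.
- With a 6-month median to progression, the median under censoring was 6.2 months throughout. As written it was 6.2 in five settings and 6.7, 6.9, 7.6 and 8.0 in the other four.
- With a 12-month median, it was 12.4 under both rules in eight settings. In the ninth (40% switching, 6-month survival after the switch) it was lower as written, 10.5 against 12.4.

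The sign is not fixed because censoring does two things: it removes the late time and it also removes an event.

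**The case against.** The strongest defence is that counting death whatever therapy came before it is a legitimate choice of estimand, that RECIST PFS (SAP 4.2.3.2) also counts death with no new-therapy rule, and that censoring at a switch can be informative because patients may switch when they are doing badly. The last part stands as a cost of the fix. The first does not carry the point: a duration that deliberately ignores later therapy needs scans to continue, and here they stop. The rule is also not applied consistently, since switchers who survive go back to the last scan. Nor does PFS settle the matter. It agrees with 4.2.3.5 on deaths but censors survivors at last contact rather than last scan, so the two endpoints do not fully match now.

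It can also be said that the affected group is small. It takes a centrally confirmed response, a switch before central progression, and then death on study. The three main cohorts enroll patients without remaining options known to help, treatment may run to 35 cycles, and imaging continues every 9 weeks after stopping without progression. That is fair, and the documents give no rate. The route is nevertheless foreseen: Protocol 6.3.2 follows patients who stop for other reasons until progression or new therapy. Scans may also stop at site-assessed progression while SAP 4.2.3 analyzes the independent reading, so a responder with site progression only can switch with none on the analysis record.

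A reader might infer that the reported duration of response is inflated. The documents do not support that: only the individual duration is sure to lengthen, and the median can move either way.

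**Conclusion.** The gap is real and minor. For responders who start new therapy without documented progression and then die, SAP 4.2.3.5 counts unscanned time on the next therapy as response and disagrees with 4.2.3.9 and 4.2.3.13 on the same scans. Switchers alive at cut-off are already handled alike under the RECIST and iRECIST response-duration rules. The size cannot be predicted from the documents: the 17% to 25% weight assumes exactly one such patient at the minimum successful responder count, and the median shifts rest on assumed switching rates and survival. Nor should a reader infer any threat to the go/no-go decision. SAP 5.6 makes ORR in the three main cohorts the only formal analysis, and SAP 5.4.4 plans no inference on secondary variables.

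**What to change.** Add one sentence to SAP 4.2.3.5: patients who start new anticancer therapy without prior progression by RECIST 1.1 are censored at their last tumor assessment before that therapy. This mirrors 4.2.3.13. Review SAP 4.2.3.2 at the same time and state how new therapy is handled for RECIST PFS, so that the two RECIST endpoints follow one rule.

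No new data are needed, because the start and type of the next cancer therapy are already collected at follow-up (Protocol 6.3.2 and 6.3.3). The cost is that some events become censored observations. The estimate then rests on slightly fewer events, and the censoring may be informative. Reporting how many responders are censored for this reason would let readers judge that.

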4.2.3.6 Overall Survival (OS)

Overall survival (OS) is defined as the time from the first dose of study treatment to the date of death due to any cause. For patients who do not die, the OS time will be censored on the date when the patient was last known to be alive. The date “last known to be alive” will be defined as the latest date of contact with the patient based on all collected evaluation dates, including the telephone contacts for the survival follow-up.

4.2.3.7 Overall response assessed through iRECIST

The categorization using iRECIST is equivalent with the categorization using RECIST 1.1 until PD. Once PD is obtained, RECIST 1.1 will stop whereas iRECIST will continue to characterize disease state also in cycles after PD.

A patient with a best overall response of either iCP or iPR is defined as a patient with an overall response according to iRECIST. A tumor measurement categorized as iCP or iPR needs a confirmed response of either iCP or iPR at least 4 weeks after the initial response assessment to be classified as best overall response iCP or iPR.

Examples of patients with an overall response are patients with the following outcome of iRECIST at cycle 3 (week 9) and subsequent every 3rd cycles:

- iSD, iSD, iPR, iPR, iSD; iPD (overall response as iPR in cycle 9 and confirmed in cycle 12)
- iSD, iSD, iSD, iCR, iCR (overall response as iCR in cycle 4)
- iSD, PD(iUPD), iPR, iPR, iSD (overall response as iPR as assessed by iRECIST in cycle 9 and confirmed in cycle 12)

Example of patients with no overall response:

- iSD, iSD, iSD, iSD, iSD, iSD, iSD, iSD, iSD
- iSD, (iUPD), iSD, iSD, iCPD
- iSD, iSD, iPR, iSD, iSD, iUPD (iPR in cycle 9 is not confirmed)
- iSD, (iUPD), iSD,

The overall response rate (ORR) using iRECIST is defined as the percentages of patients that are classified as overall responders assessed through iRECIST as described above.

4.2.3.8 Immune Best Overall Response (iBOR)

The immune best overall response (iBOR) is the best timepoint response recorded from the start of the study treatment until the last assessment of tumor response recorded during study period or the start of post treatment cancer therapy (whichever is sooner), taking into account any requirement for confirmation. iUPD will not override a subsequent best overall response of iSD, iPR, or iCR, meaning that iPR or iSD can be assigned (timepoint response or iBOR) even if new lesions have not regressed, or if unequivocal progression (non-target lesions) remains unchanged, providing that the criteria for iCPD are not met. Table 3 gives scenarios for assignment of iBOR (Seymour (2017)).

Table 3 Scenarios of assignments of best overall response using iRECIST

	Timepoint response 1	Timepoint response 2	Timepoint response 3	Timepoint response 4	Timepoint response 5	iBOR
Example 1	iCR	iCR, iPR, iUPD, or NE	iCR, iPR, iUPD, or NE	iUPD	iCPD	iCR
Example 2	iUPD	iPR, iSD, or NE	iCR	iCR, iUPD, or NE	iCR, iPR, iSD, iUPD, iCPD, or NE	iCR
Example 3	iUPD	iPR	iPR, iSD, iUPD, or NE	iPR, iSD, iUPD, NE, or iCPD	iPR, iSD, iUPD, NE, or iCPD	iPR
Example 4	iUPD	iSD or NE	iPR	iPR, iSD, iUPD, or NE	iPR, iSD, iUPD, iCPD, or NE	iPR
Example 5	iUPD	iSD	iSD, iUPD, or NE	iSD, iUPD, iCPD, or NE	iSD, iUPD, iCPD, or NE	iSD
Example 6	iUPD	iCPD	Any	Any	Any	iCPD
Example 7	iUPD	iUPD (no iCPD)	iCPD	Any	Any	iCPD
Example 8	iUPD	NE	NE	NE	NE	iUPD

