In patients who have initial evidence of radiological PD, it is at the discretion of the treating physician whether to continue a patient on study treatment until repeat imaging is obtained. This clinical judgment decision should be based on the patient's overall clinical condition, including performance status, clinical symptoms, and laboratory data.

iRECIST criteria include the above RECIST 1.1 derived criteria (see Table 11 and Table 12 below) with the proviso that the increase in tumor burden must be shown to increase, but in the case of iUSD, iUPR or iCR, the assessment time bar is reset.

For target lesions, iCR, iPR and iSD can all be assigned after iUPD has been documented as long as iCPD has not been confirmed. Progression is confirmed in the target lesion category if the next imaging assessment after iUPD (4-8 weeks later) confirms an increase in the sum of target lesions dimensions of greater than 5 mm. However, iCPD is not met if the imaging assessment after iUPD is followed by CR, PR or SD (compared to baseline as defined in RECIST 1.1). The status is reset and assessment continues. Please note this is different from RECIST 1.1

Thus iUPD can be assigned on multiple occasions, as long as iCPD is not declared.

Table 11 Comparison of RECIST 1.1, iRECIST and irRECIST

	RECIST 1.1	iRECIST	irRECIST
Definitions of disease: numbers, sites and target or non	Measurable are diameters greater than 10 mm (15 for nodes maximum of 5 (2 per organ))	No change from RECIST 1.1	No change from RECIST 1.1
CR, PR or SD	Cannot have met criteria for progression	Can have had iUPD (more than once) but not iCPD before iCR, iPR or iSD	Use of terminology based around RECIST 1.1
Confirmation of CR or PR	Only in non-randomized studies	As per RECIST 1.1	As per RECIST 1.1
Confirmation of SD	Not required	As per RECIST 1.1	As per RECIST 1.1
New lesions	Progression: recorded but not measured	iUPD but only becomes iCPD if on the next scan there are new lesions or the size increases by greater than 5 mm	Unclear
Confirmation of progression	Not required	Required	Required
Consideration of clinical status	Not required	Clinical stability considered at iUPD to decide treatment continuation	As iRECIST without terminology considering unconfirmed findings

Table 12 Trajectory of progression in iRECIST

Target Lesions: iCR, Non-target: iCR, no new lesions	iCR	iCR
Target lesions: iCR, Non-target: non iCR/non iUPD, no new lesions	iPR	iPR

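### SAP Table 3 allows an iBOR of iCR or iPR on a single unconfirmed reading, contrary to the SAP's own text and the protocol's confirmation rule

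*SAP*

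**What the plan says.** SAP 4.2.3.8 defines iBOR as the best timepoint response over the study period, "taking into account any requirement for confirmation". It then refers to an eight-row table: "Table 3 gives scenarios for assignment of iBOR". Table 3 shows no footnote or condition on confirmation. Four of its rows end in a response:

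- Example 1: iCR at timepoint 1, then "iCR, iPR, iUPD, or NE" at timepoints 2 and 3, then iUPD and iCPD. iBOR is iCR.
- Example 2: iUPD first, iCR at timepoint 3, possibly iUPD or NE at timepoint 4, and "iCR, iPR, iSD, iUPD, iCPD, or NE" at timepoint 5. iBOR is iCR.
- Example 3: iUPD, iPR, a third reading that may be iSD, iUPD or NE, then "iPR, iSD, iUPD, NE, or iCPD" at each of timepoints 4 and 5. iBOR is iPR.
- Example 4: iUPD, then iSD or NE, then iPR, a fourth reading that may be iSD, iUPD or NE, and "iPR, iSD, iUPD, iCPD, or NE" at timepoint 5. iBOR is iPR.

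The rest of the plan asks for confirmation. SAP 4.2.3.7 needs a second iCR or iPR at least 4 weeks after the first before a patient's iRECIST best overall response is iCR or iPR. It lists this sequence as a non-responder: "iSD, iSD, iPR, iSD, iSD, iUPD (iPR in cycle 9 is not confirmed". SAP 4.2.3.11 says in passing that confirmation is required for an immune best overall response of iCR or iPR, and 4.2.3.12 requires it for time to immune response. Protocol Table 11 (section 9.1.4) has confirmation of CR or PR apply "Only in non-randomized studies" and carries the rule over to iRECIST. Protocol 12.3 states that the study is not randomised.

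**The concern.** The text and the table give two rules for one quantity, and the SAP does not say which prevails. From the same data, a programmer working from the text and one working from Table 3 would produce different iBOR listings.

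Under the table, one patient could be iPR in the iBOR summary and a non-responder in the iRECIST ORR reported for the same cohort. Duration of iBOR (4.2.3.9) runs from the date iBOR is first documented, so for such a patient it would start at an unconfirmed response. Duration of immune response (4.2.3.13) is restricted to overall immune responders and would leave the same patient out. The SAP also does not say what label an unconfirmed iCR or iPR should receive.

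**Working it through.** The plan gives no numerical figure for iBOR to reproduce, so the check lists the sequences that Table 3 allows and applies the 4.2.3.7 rule to them.

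**Step 1: test the rule on the SAP's own examples.** A sequence counts as a response if an iCR or iPR is followed by another iCR or iPR at least 4 weeks later, with no iCPD in between. Scheduled scans are 9 weeks apart, so any two scheduled readings meet the spacing. Applied to the seven worked sequences in 4.2.3.7 (reading iPD in the first as iUPD), the rule returns the SAP's answer for all seven.

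**Step 2: count the allowed sequences.** Multiply the number of options at timepoints 1 to 5. Then repeat, keeping only options that leave exactly one iCR or iPR in the sequence.

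| Table 3 row | iBOR | All sequences | Exactly one iCR/iPR |
|---|---|---|---|
| Example 1 | iCR | 1×4×4×1×1 = 16 | 1×2×2×1×1 = 4 |
| Example 2 | iCR | 1×3×1×3×6 = 54 | 1×2×1×2×4 = 16 |
| Example 3 | iPR | 1×1×4×5×5 = 100 | 1×1×3×4×4 = 48 |
| Example 4 | iPR | 1×2×1×4×5 = 40 | 1×2×1×3×4 = 24 |
| Total | | 210 | 92 |

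None of the 92 can be a response under 4.2.3.7, because there is no second reading to confirm the first.

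**Step 3: allow for how confirmation is read.** If any later iCR or iPR before iCPD confirms, 4 + 16 + 51 + 24 = 95 sequences are unconfirmed. The extra 3 in Example 3 have a second iPR only after iCPD. If the very next assessment must confirm, 8 + 24 + 72 + 30 = 134 are unconfirmed. The other 76 to 115 sequences are confirmed and keep a response label. These are counts of patterns, not probabilities.

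**Step 4: compare like with like.** In 4.2.3.7, one iPR followed by iSD and iSD is not a response. In Example 4, iUPD, iSD, iPR, iSD, iSD gives iBOR of iPR. The response part of the two histories is the same and the conclusions are opposite.

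**Step 5: size per patient.** One patient labelled differently moves the iBOR response share away from the iRECIST ORR by 1/n. In the three main cohorts n runs from 25 (the smallest Simon total) to 28 (the largest recruited number): 1/28 = 3.6 points and 1/25 = 4.0 points.

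**The case against.** The best defence is that the SAP has already chosen confirmation. The definition in 4.2.3.8 mentions it, 4.2.3.11 states it for iBOR by name, and Table 3 is introduced only as scenarios, with a publication cited. On that view the table illustrates the text and does not override it. This stands to the extent that a wrong label arises only if someone follows the table in preference to the text. It does not remove the conflict: the columns are timepoint responses, nothing says the entries are already confirmed, and all four response rows return a result that the text forbids.

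A reader might go further and infer that every patient with a single unconfirmed iPR or iCR is affected, or that iBOR will exceed the iRECIST ORR by several points in a cohort. The documents do not support either. Example 1 begins with iCR and Examples 2 to 8 begin with iUPD; no row begins with iSD or iPR. The non-responder sequence quoted from 4.2.3.7 begins with iSD, so it matches no row, and only the text governs it. A cohort-level gap would need the number of unconfirmed responses after a first-scan iUPD, or of unconfirmed first-scan iCRs. The documents give neither, and the gap could be zero. Patients who are clinically unstable at first progression stop treatment and need no repeat scan (Protocol 9.1.5), which narrows the group further.

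It is also fair that iBOR is exploratory (SAP 4.2.2.3) and only described (5.6.3).

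**Conclusion.** The inconsistency is real and limited. Table 3, Examples 1 to 4, permits iBOR of iCR or iPR without confirmation, against SAP 4.2.3.7, 4.2.3.8 and 4.2.3.11 and Protocol Table 11.

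The consequence is conditional on Table 3 being followed. It reaches only patients with an unconfirmed iCR at the first scan, or with iUPD at the first scan and one later unconfirmed iCR or iPR. Each would add about 3.6 to 4.0 points to the difference between the iBOR response share and the iRECIST ORR, assuming 25 to 28 evaluable patients; a smaller evaluable population would make the step larger. The number of such patients cannot be predicted from the documents.

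The RECIST 1.1 primary endpoint has its own explicit confirmation rule (SAP 4.2.3.1) and does not use iBOR. The Simon tests, alpha and power are therefore untouched. The point is still worth correcting, because a stated rule gives a wrong label.

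**What to change.** Either restrict Examples 1 to 4 to sequences in which the iCR or iPR is confirmed, or add a footnote to Table 3 saying that iCR and iPR require a further iCR or iPR at least 4 weeks later, as in 4.2.3.7. The same footnote should say whether an intervening NE, iSD or iUPD breaks confirmation, since the count above moves between 95 and 134 on that question.

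Also state the label for an unconfirmed iCR or iPR, for example iSD if assessed at 6 weeks or later, in line with the limit already in 4.2.3.11.

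The cost is one table edit or footnote and one derivation rule, best settled before database lock. The reported iBOR response share may be slightly lower as a result.
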